NHS REC National Health Service Research Ethics Committee

NHS R&D National Health Service Research & Development

Participant An individual who takes part in a clinical trial

PI Principal Investigator

PIS Participant Information Sheet

QA Quality Assurance
QC Quality Control

RCT Randomised Controlled Trial

REC Research Ethics Committee

SAE Serious Adverse Event

SDV Source Document Verification
SOP Standard Operating Procedure

Sequential Organ Failure Assessment

SSA Site Specific Assessment

SOFA

TMG Trial Management Group

TSC Trial Steering Committee

4. SUMMARY/SYNOPSIS

Short Title	ACIT II
Methodology	Multicentre, prospective observational cohort study
Research Sites	Royal London Hospital, Bart's Health NHS Trust John Radcliffe Hospital, Oxford University Hospitals NHS Trust Royal Victoria Infirmary, Newcastle Upon Tyne Hospitals NHS Trust Salford Royal Hospital, Salford Royal NHS Foundation Trust
Objectives/Aims	A prospective, observational cohort study designed to investigate the molecular mechanisms activated by traumatic injury and how these relate outcome and the effect of early therapies to treat trauma haemorrhage.
Number o Participants/Patients	f 5,000 patients

School of Medicine and Dentistry	University of London						
Inclusion Criteria	All trauma patients who either:						
	(1) Receive prehospital treatment by London Air Ambulance (Bart's Health) and are admitted to a study site hospital (adults only)						
	(2) Admitted to a study site hospital and require a full trauma team activation e.g. conveyed by a land ambulance service or self-presentation to the emergency department (adults and children)						
Exclusion Criteria	Any patient who fulfils any of these criteria will not be considered for inclusion in the study:						
	Transfers from other hospitals						
	Burns >5% total body surface area						
	 >120 mins have lapsed since time of injury Deemed inappropriate for recruitment by an independent clinician (e.g. mass casualty event or futility) 						
Statistical Methodology &	Not applicable						
Analysis							
Proposed Start Date	With immediate effect after ethical (REC) approval of substantial						
	protocol amendment to version 8.0 on 16 th July 2024						
	(ACIT II study has been active since January 2008)						
Proposed End Date	Open ended						
Study Duration	Ongoing						

5. INTRODUCTION

5.1 Background

Trauma remains one of the world's biggest contributors to the global burden of disease, and is increasing in both incidence and severity, with over 6 million deaths worldwide as the result of injury.(1) It is the leading cause of death in those under the age of 45 years, although as the population ages it is increasingly affecting the elderly. Historically, uncontrolled haemorrhage, traumatic brain injury, and multiple organ failure have been the major causes of mortality and for the most part this remains unchanged. Of these, uncontrolled haemorrhage is the leading cause of preventable death.(2) Over the past 100 years, advances in emergency medical systems, trauma surgery and trauma resuscitation have allowed patients who would otherwise have died on the streets to reach hospital and receive emergent treatment of their life-threatening injuries. More recently there has been an explosion in our understanding of trauma sciences with significant advances made over the last decade in managing bleeding. However to date there no cure for organ failure, only supportive care. There remains much to be discovered if the trauma community is to further improve outcomes from injury and address the adverse sequela of immune dysfunction and bleeding in order to create new survivors.

Patients who are bleeding develop a disorder of the blood clotting system which leads to further bleeding, shock and potentially irreversible physiological derangements that lead to death.(3) Using early ACIT II data we have been able to characterise some elements of the global clotting disorder known as trauma-induced coagulopathy (TIC)(4-7) but many more questions remain unanswered e.g. how many different patterns of bleeding disorder exist after trauma, how they arise and what are the best diagnostic tests for rapid identification. Preliminary findings from the ACIT II have highlighted four clinically important bleeding phenotypes but currently it is impossible to fully stratify patients, assess the entire derangement in clotting or degree of dysfunction. We have shown through the introduction of viscoelastic haemostatic assays such as Rotational Thromboelastometry (ROTEM), some elements of ATC can be detected rapidly but these assays are unable to provide a complete picture of clotting with platelet function and clot breakdown pathways poorly quantified by this technology.(4, 8) As such there remains only limited tools to guide transfusion therapy. We have shown that many patients who are bleeding continue to get inadequate numbers of blood products to correct coagulopathy.(9) Conversely patients may be given blood products unnecessarily leading to all the complications associated with blood transfusion, including depression of the immune system,(10) which is critical in major trauma patients.

Although they may survive this critical phase of their care, many of these patients will still die. Death, which usually occurs one to six weeks later, is due to a progressive failure of body systems — a syndrome called multiple organ dysfunction syndrome (MODS).(11) There is currently no specific treatment for MODS. Patients are supported on ventilators, dialysis machines and other organ support devices while the process runs its course. Patients who survive MODS may spend months in hospital, years in rehabilitation, and are usually left with some permanent disability.(11)

Recent studies suggest that this late mortality due to MODS may be due to the body's responses to tissue damage and to blood loss that occur immediately following injury.(12) There is a significant body of both basic science and clinical evidence that implicates the activation and dysregulation of the coagulation and inflammatory systems in the development of MODS.(13) However, most of this data comes from research into sepsis which may not be directly translatable. The mechanisms for the activation of the relevant pathways in trauma, and their relationship to clinical disease and outcomes have yet to be delineated. Identification of these key pathways will provide new directions for drug development and perhaps a specific treatment for post-traumatic MODS, either through organ protection or organ restorative therapies.

We postulate two mechanisms for the activation of these systems in trauma: tissue damage itself, and cellular hypoperfusion.

Tissue damage

A number of studies including the first from our group at the Royal London Hospital, (14) have shown that trauma patients may arrive in the emergency department with severely deranged blood coagulation. (15) Significant tissue damage (in conjunction with severe blood loss) results in a reduced ability to form and maintain clots, leading to further bleeding, through an endogenous process termed acute traumatic coagulopathy (ATC). (16) Patients with this coagulopathy are three to four times more likely to die than those without. (7, 14) The incidence of coagulopathy was closely related to the severity of injury, and not to the volumes of fluid administered, suggesting that the injury load itself was responsible for the activation

of the coagulation systems. The precise mechanisms by which tissue injury activates the coagulation and inflammatory systems have yet to be fully characterised.

Tissue hypoperfusion / hypoxia

Ischemia following haemorrhagic shock is known to lead to MODS and increased mortality.(11) Several studies have shown that the severity of shock on admission correlates with eventual outcome. The duration of tissue ischemia, as measured by base deficit and lactate, and even sub-clinical tissue ischemia which persists for over 12 hours has a mortality is 38%, over twice that of patients who do not suffer a prolonged ischemic episode.(17) Tissue hypoxia leads to endothelial injury and priming of cellular and humoral components of the inflammatory pathways.(18)

It is believed that haemorrhagic shock and direct tissue injury are independently associated with the development of a hyperinflammatory state that may result in MODS. Preliminary genetic analysis of data from 70 trauma patients collected through the ACIT II platform has identified early genetic changes with associated acute immune dysfunction and the development of MODS.(12) Further, ACIT II data has identified a previously undescribed acute cardiovascular failure (19, 20) linked to injury remote from the heart, and represents an important novel area for future investigation.

Coagulopathy and injury pattern

There is increasing recognition that disorders of blood clotting after trauma may differ according to injury patterns e.g. multisystem injury with major haemorrhage versus isolated traumatic brain injury. These clotting disorders in the latter patients are poorly characterised, poorly understood and associated with worse outcomes. (21,22) Recent studies have suggested that therapies targeting coagulation may lead to improved outcomes for patients with brain injuries, offering a potential new therapy for a condition where treatments and outcomes have changed very little in the last 20 years (23-25). The specific abnormalities, mechanisms, and treatment options for blood clotting disorders in this group remain unknown.

5.2 Rationale

The entire pattern of activation of the inflammatory and coagulation systems has not been fully elucidated in trauma patients, and it remains unknown if and how this results in MODS and death. We hope that this study will allow us to fully characterise trauma-induced coagulopathy and allow us to better target blood and component therapy by identifying clinically useful markers of early coagulopathy and the response to transfusion. Conversely, we expect that identifying those patients without coagulopathy might suggest that specific measures of coagulation during a massive transfusion would lead to a reduction in the total number of blood products transfused and a reduction in the number of complications.

We further hope that we will identify key junctures in the pathways that could be targeted for drug discovery and development programs. This will allow us to better understand which patients may benefit from the novel procoagulant agents e.g. recombinant clotting factors, factor concentrates as well as antifibrinolytic drugs e.g. tranexamic acid.

Serial sampling from multiple tissues/organs, early after the disease onset for the first seven days, will provide a unique resource for high impact research in understanding the interplay between organ systems in the acute response to injury. Further, understanding the interplay between coagulation and acute inflammation after trauma may allow us to intervene early to avoid the late complications of MODS, thrombotic episodes and immune dysfunction and help create new survivors from major injury.

Injury is a unique model in which to investigate sterile inflammation, with a clear time point of disease onset and unrivalled potential for integration of "omics" research to study the activation of inflammatory pathways. Rapid onset and relative rapid resolution of disease (hours, days) provides the opportunity to evaluate response to therapy or prophylaxis. Characterising how the body recognises injury, and identifying early biomarkers of organ dysfunction, will provide opportunity for modulating the acute immune response to protect cells or organs. An in depth understanding of the immune response will facilitate the design of novel biologic or cellular therapeutics for precision medicine. Biomarker signature profiles will aid development of specific devices to detect and monitor organ dysfunction for earlier diagnosis or prevention of harmful long-term effects.

Research to date has predominantly focused on adult trauma patients, yet there is an expanding geriatric population who are increasingly sustaining multisystem injuries on the background of poor physiological reserve. This requires a greater understanding of the physiological responses in senescence.

Prehospital sampling

Findings from samples collected within minutes of injury, and our own preliminary data from ACIT II suggest a number of coagulation and inflammatory pathways are activated and/or deranged in the hyperacute period after trauma e.g. <60 minutes. Expanding our research capability to the patient as close to the point of injury will help characterise and understand early physiological and biochemical changes. Understanding whether these very early changes determine clinical outcome, and whether there are novel ways to modulate the response to injury are key research priorities.

Inclusion of paediatric patients

The paediatric population are grossly under-represented in human discovery trauma science with the vast majority of studies specifically excluding children. Trauma however remains a significant disease burden in this population group. Injury profiles, physiological response and management strategies for children are different compared to adults. In part this is due to their physical and physiological characteristics e.g. body size, head size, fat proportion, and reduced bone strength but increased bone pliability. These factors influence how energy from an accident is distributed and consequently children can have severe internal organ injury without bony fractures. Children are much more susceptible to hypothermia, which is known to worsen coagulopathy and organ dysfunction. In addition, clinical examination and vital signs can often be misleading as children are able to physiologically compensate for blood loss to a greater extent than adults. Classically paediatric patients may display a relatively normal physiology up to a point, before sudden and catastrophic circulatory collapse.

The vast majority of clinical evidence which guides trauma practice is translated from adult patients without dedicated paediatric evaluation. Characterisation of key pathways in coagulopathy, organ injury and MODS and therefore evidence to guide management of trauma and haemorrhagic shock in children is wholly inadequate. An important evidence gap exists in our understanding of the paediatric response to injury and blood transfusion, drivers

for organ dysfunction and whether all "adult therapies" e.g. tranexamic acid produce similar effects in the paediatric trauma population.

6. STUDY OBJECTIVES

6.1. Study Aims & Hypotheses

AIM 1: Coagulopathy and Massive Transfusion

Characterize the key derangements and describe trauma specific phenotypes in coagulation, fibrinolytic, platelet and endothelial cell function following major injury; determine the response to blood component therapy and anti-fibrinolytic medication; and further characterize the subsequent hypercoagulable state.

Hypothesis ACIT: 1A

Acute traumatic coagulopathy is caused primarily by tissue hypoperfusion which leads to systemic activation of anticoagulant and fibrinolytic pathways as well as global platelet dysfunction. Pathways of activation and dysfunction vary according to patient specific (e.g. age) and injury specific (e.g. site of injury, presence/duration of hypoperfusion) factors.

Hypothesis ACIT:1B

Subsequent transfusion of red cells, blood component therapy and antifibrinolytic drugs (e.g. tranexamic acid) have specific effects on the acute coagulopathy, which may be beneficial or harmful dependent on the current clinical state.

Hypothesis ACIT: 1C

Early coagulopathy leads to exhaustion of the anticoagulant system, up-regulation of antifibrinolytic systems and altered platelet function, resulting in a hypercoagulable state which is associated with thrombotic events and organ dysfunction.

Hypothesis ACIT 1D:

Children develop an acute traumatic coagulopathy that is distinct from that observed in adults. The coagulopathy can be identified and characterized with viscoelastic testing and coagulation biomarkers and platelet function assays.

Hypothesis ACIT 1E:

Acute traumatic coagulopathy occurs within minutes after injury and can be detected in the prehospital phase of care. Diagnostics for hyperacute identification can stratify patients for targeted treatment of precise derangements in coagulation.

Hypothesis ACIT 1F:

Patients with traumatic brain injury develop a coagulopathy that is distinct from that observed in bleeding trauma patients. The coagulopathy can be identified and characterised with viscoelastic testing, coagulation biomakrers and platelet function assays.

AIM 2: Development of Organ Injury

To elucidate the effect of derangements in coagulation, fibrinolytic, platelet and endothelial cell function on the inflammatory response and the development of acute organ injury (e.g. lung, kidney, cardiac), multiple organ dysfunctions (MODS), and death.

Hypothesis ACIT: 2A

There is a dose-dependent effect of the severity of trauma on coagulation, fibrinolytic, platelet and endothelial cell function. These correlate with activation of a pathological systemic inflammatory response that leads to acute organ injury (e.g. lung, kidney, cardiac) and MODS.

Hypothesis ACIT: 2B

There is a dose-dependent effect of the degree and duration of tissue hypoperfusion on coagulation, fibrinolytic, platelet and endothelial cell function. These correlate with activation of a pathological systemic inflammatory response that leads to acute organ injury (e.g. lung, kidney, cardiac) and MODS.

Hypothesis ACIT: 2C

While tissue trauma (ACIT:2A) and cellular hypoperfusion (ACIT:2B) are different initiators, the resulting activation of the coagulation and inflammatory systems is identical and is the final common pathway in acute organ injury and MODS. Tissue trauma and cellular hypoperfusion have an additive effect on the development of organ injury and MODS.

Hypothesis ACIT:2D

Children with major trauma exhibit a specific immunological signature in response to tissue damage and blood loss that differs from adults. Particular responses are either associated with or protective for developing organ injury and MODS.

Hypothesis ACIT 2E:

Cellular pathways and biochemical signalling that produce organ injury and MODS occurs within minutes after injury and can be detected in the prehospital phase of care. Diagnostics for hyperacute identification can stratify patients for organ protective or organ restorative therapies.

AIM 3: Prediction models in major trauma

To develop a prediction model for massive transfusion requirements and the development of organ injury in following trauma in adult and paediatric patients.

Hypothesis ACIT:3A

Massive transfusion requirements can be predicted by initial physiological variables and immediate analysis of coagulation parameters. Conversely, the requirement for blood component therapy might be reduced by targeted measurement of coagulation function and biomarkers during transfusion.

Hypothesis ACIT:3B

Acute organ injury (e.g. lung, kidney, cardiac) can be predicted in the first hours after trauma based on trauma severity scores, tissue damage, severity and duration of tissue ischemia,

with biochemical markers of coagulation or inflammation. Identify specific markers which may be clinically relevant.

AIM 4: Genomic, proteomic and lipidomic analysis

To process and store samples for subsequent proteomic, transcriptomic, lipidomic and genomic techniques to identify new loci for investigation, targeting drug discovery and identification of genetic susceptibility to poor outcome following trauma.

Hypothesis ACIT:4A

There are signature transcriptomic, proteomic and lipidomic profiles associated with the risk of post-traumatic MODS and other adverse outcomes. Specific changes in circulating leukocytes and parenchymal cells occur in organs remote from the injured site and are associated with MODS.

Hypothesis ACIT: 4B

Children develop a specific transcriptomic and proteomic response to tissue trauma and hypoperfusion that is protective against post-traumatic organ injury and MODS.

AIM 5: Trauma DNA Bank

To process and store samples for subsequent DNA typing and analysis. There appears to be a background race and genetic susceptibility to the effects of trauma. These alterations may well lie within the coagulation and inflammatory systems. Early identification of patients at risk may, in the future, allow therapy to be targeted depending on patients' racial background or even specific genetic make-up.

Hypothesis ACIT:5A

There are genetic mutations of coagulation and inflammatory genes (e.g. Factor V Leiden, Prothrombin 20210, Mannose Binding Lectin) that may protect against or increase susceptibility to the effects of tissue trauma and hypoperfusion.

Hypothesis ACIT:5B

There are Haplotype-specific (and thus race-related) variations in susceptibility and response to tissue trauma and hypoperfusion.

6.2. Primary Outcomes

For both adult and paediatric populations the outcome measures will be:

Blood products transfused in the first 24 hours

Incidence & severity of acute organ injury & MODS

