6.3. Secondary Outcomes

For both adult and paediatric populations the outcome measures will be:

- 28-day mortality
- · Ventilator free days
- Length of hospital and critical care stay
- · Thrombotic events
- Requirement for organ support (artificial ventilation, renal replacement therapy, inotropic support)
- Infection organ specific and each episode detailed
- Transfer destination at discharge e.g. home, other medical facility, rehabilitation unit
- Quality of Life at 28 days and 1 year (EQ5D questionnaire and extended Glasgow Outcome Scale for adults, age appropriate PedsQL for paediatric patients)

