7.3. Inclusion Criteria

Patients eligible for screening are all trauma patients of any age including children:

requiring treatment by the London Air Ambulance medical team (adults only) **and/or**requiring admission to the Emergency Department with a full trauma team
activation (adults and children)

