9.3 Schedule of study interventions

Study Activity	Prehospital	Emergency Department	HR 24	HR 48	HR 72	Day 3-7	Day 7	Day 8-288 - 28 days	Discharge/	1-year follow up
Demographics	Adults only	Х								
Injury characteristics	Adults only	Х								
Physiological observations	Adults only	Х	Х	Х	Х	Х	Х	Х		
Organ score (SOFA)			Х	Х	Х	X	X	X	X	
Infections			Х	Х	Х	Х	Х	Х		
Thrombotic Events			Х	Х	Х	Х	Х	х		
Adverse events			Х	Х	х	Х	Х	х		
Blood Sampling*	Adults only	Х	Х		Х		Х			
Muscle biopsy			(X)	(X)	(X)	(X)				
Quality of Life assessment									Х	Х
GOS-E									Х	Х

^{*}All patients with have one blood sample taken on admission at the same as routine clinical blood tests. Bleeding patients requiring blood transfusion will have further samples taken after transfusion of the 4th, 8th and 12th unit of red blood cells in conjunction with routine clinical blood tests. (X) Muscle biopsies will only be taken during a planned or emergency surgical procedure as part of routine clinical care

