9.7. Patient withdrawal

Each participant has the right to withdraw from the study at any time and for any reason without prejudice to his or her future medical care by the Investigator or at the institution.

Every reasonable effort will be made to maintain protocol compliance and to retain patient participation in the study consistent with the provisions of informed consent and good clinical practice. Additionally the PI may withdraw the participant. The following are potential reasons why a patient may be withdrawn from the study:

- Withdrawal of consent: the patient, the patient's authorised representative, independent physician, or designated individual who had provided initial consent to enter the study may withdraw consent at any time throughout the duration of the trial, without prejudice to future medical care and treatment.
- Retrospective exclusion: If a patient is deemed to not meet one or more of the inclusion/exclusion criteria in retrospect they will be withdrawn from the study.
- Major protocol deviation from the study design by the participant, observed or suspected by the investigator.
- Administrative: the sponsor or monitoring committees decide to terminate or discontinue the study.

 The participant's health would be jeopardised by continued participation and is withdrawn at the discretion of the investigator.

Data collected up to the point of withdrawal will be retained. To safeguard the participants' rights, the minimum personally-identifiable information possible will be used.

Participants will be asked whether samples already collected can be retained for use in the study. Where a participant consents to storage and use of their samples, they will be asked to sign a consent form reflecting this agreement.

Any samples obtained from withdrawn participants who do not consent to storage or use of their samples will be discarded in accordance with the local NHS Trust standard procedures. Samples sent to the central laboratory at Queen Mary University London will also be discarded.

All participants withdrawn from the study will be managed in accordance with the hospital's standard procedures.

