SWiFT is a multi-centre, prehospital randomized control trial (RCT) to evaluate whether leukocyte-depleted Whole Blood (WB) stored at $2-6^{\circ}$ C is superior to standard of care (red cells and any form of plasma) in bleeding trauma patients. A total of 848 patients (424 in each arm) will be recruited over a 2-year period, with recruitment planned to start in June 2022. The trial is sponsored by NHS Blood and transplant (NHSBT) and funded jointly by NHSBT, nine air ambulance charities and UK Defence Medical Services. The primary objective of the trial is to determine whether WB transfusion (platelet rich) is better than standard care (blood component transfusion and/or lyosophilized plasma) in reducing 24 hr mortality or massive transfusion (defined as >10 units of any blood component) in patients with life-threatening haemorrhage.

International guidelines consider platelet transfusions integral to a massive haemorrhage protocol to treat trauma-induced coagulopathy although the mechanism by which platelets support coagulation and improve outcome are largely unknown. In severe

trauma patients, both thrombocytopenia and platelet dysfunction, as measured by decreased aggregation in response to agonists, have been shown to be directly associated with increased mortality. Even in the presence of a normal platelet count upon admission, dysfunction occurs in around half of critically injured patients and is an independent predictor of in-hospital mortality.

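### The synopsis, 7.2 and 7.3 disagree on whether air-ambulance patients who die before admission belong to the cohort; the 24-hour product count is also cut short by early death

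*Protocol*

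**What the plan says.** **Eligibility.** Inclusion criterion (1) in the synopsis covers patients treated before hospital by the air ambulance "and are admitted to a study site hospital (adults only"). Section 7.2 restricts enrolment to air-ambulance patients whose conveyance to a study site is planned, or patients arriving by other means with a trauma team activation. Section 7.3 lists patients "requiring treatment by the London Air Ambulance medical team (adults only"), joined by and/or to emergency department admission with a full trauma team activation.

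**Timing.** Under 7.2, eligible patients are enrolled automatically after screening, either before hospital or on arrival. Section 9.4.1 has the air-ambulance sample drawn when the team arrives.

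**Withdrawal.** Section 9.7 states: "If a patient is deemed to not meet one or more of the inclusion/exclusion criteria in retrospect they will be withdrawn from the study". Data collected before withdrawal are kept.

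**Outcomes.** Section 6.2 names two primary outcomes, "Blood products transfused in the first 24 hours" and "Incidence & severity of acute organ injury & MODS", without saying how death bears on either. Section 6.3 lists "28-day mortality" separately as a secondary outcome. In the section 9.3 schedule the SOFA row is first marked at hour 24, and under 9.4.4 daily follow-up ends at Day 28, discharge or death. Appendix 4 describes the SWiFT trial's objective as "reducing 24 hr mortality or massive transfusion (defined as >10 units of any blood component").

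**The concern.** Admission to hospital happens after enrolment for anyone sampled at the scene. An inclusion criterion that requires it therefore selects on survival. The patients lost would be those who deteriorate fastest, whose prehospital samples are likely to be among the most abnormal. Hypotheses 1E and 2E claim that coagulopathy and organ-injury signalling begin in the first minutes and can be detected before hospital, so this is the group they can least afford to lose. Whether a patient counts would also depend on which section the research team consults.

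The transfusion outcome has a milder form of the same problem. A patient who bleeds to death at two hours has a 24-hour count made up of the few units given by then. Aim 3 and hypothesis 3A concern transfusion requirements. For that patient, units received are a poor measure of requirement.

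**Working it through.** The protocol states no figure to reproduce. Section 10 says a power calculation does not apply, and no early-death, massive-transfusion or MODS rate is given for this cohort. The eligibility check is a comparison of texts.

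| Adult treated and sampled by the air ambulance | Synopsis | 7.2 | 7.3 |
|---|---|---|---|
| Conveyed and admitted to a study site | in | in | in |
| Conveyance to a study site planned, dies before admission | out | in | in |
| No conveyance to a study site planned (e.g. dies at scene) | out | out | in |

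The second row is the important one. The patient was validly enrolled under 7.2, a sample exists, and the synopsis criterion then fails. Section 9.7 turns that failure into withdrawal. The third row shows that 7.3 alone is wider than 7.2.

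**Transfusion count.** All rates here are assumed. Let s be the share of patients who truly need a massive transfusion and f the fraction of those who die before reaching the threshold. The observed share is s × (1 − f). With s = 10%:

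- f = 10%: 10% × 0.90 = 9%
- f = 30%: 10% × 0.70 = 7%
- f = 50%: 10% × 0.50 = 5%

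**MODS, only if early deaths were scored as event-free.** The protocol does not say this; the calculation shows how much would hang on it. Let m be the MODS risk among patients who live to be scored and d the risk of early death, in a high-risk (1) and a low-risk (0) group. The observed risk ratio is (1 − d1) × m1 / ((1 − d0) × m0). Assume m0 = 20% and m1 = 40%, a true ratio of 2.0:

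- d0 = 2%, d1 = 5%: 0.95 × 0.40 / (0.98 × 0.20) = 1.94
- d0 = 5%, d1 = 10%: 0.90 × 0.40 / (0.95 × 0.20) = 1.89
- d0 = 5%, d1 = 20%: 0.80 × 0.40 / (0.95 × 0.20) = 1.68
- d0 = 5%, d1 = 30%: 0.70 × 0.40 / (0.95 × 0.20) = 1.47

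In these scenarios the association is diluted towards no effect but is neither abolished nor reversed.

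**The case against.** **On eligibility.** Section 7.3 opens by describing patients eligible for screening, and 7.2 limits who is enrolled, so the two can be read together. That narrows the conflict but does not remove it. Section 7.2 closes by making enrolment depend on the criteria listed after it, and the synopsis still asks for admission where 7.2 asks for planned conveyance. Section 11.1[f] keeps patients who die before consent can be sought, on the professional consultee's consent. This suggests no intention to discard early deaths, but it is a consent rule and does not settle eligibility. Section 9.7 keeps data gathered before withdrawal, so the loss is of cohort membership and not necessarily of the record. The futility exclusion can remove some of the sickest patients under any wording, and aligning the text will not bring those back.

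**On the outcomes.** A reader might infer that early deaths are counted as having no MODS, and that the prediction models would therefore learn that the worst physiology is harmless. The documents do not support this. They are silent on the point. A patient who dies before hour 24 has no scheduled SOFA score, which is not a score of zero, and 6.2 does not name SOFA as the only source. Handling of unscored MODS can properly sit in a statistical analysis plan that is not shown here.

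A reader might also want the transfusion outcome replaced by the SWiFT composite. SWiFT is a randomised superiority trial, whereas this is a mechanistic cohort. Section 11.5 places brain-injury deaths as well as haemorrhage deaths in the first few days, so a composite would put some brain-injury deaths into a transfusion model. That is a fair reason to keep the stated outcome and make any composite supportive.

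**Conclusion.** The eligibility conflict is established from the text alone and needs no assumption. Under the synopsis and 9.7, air-ambulance patients who are enrolled and sampled but die before admission would be withdrawn; under 7.2 they stay. The number affected cannot be derived from the documents. It is probably small, because only adults treated by one air-ambulance service who die between enrolment and admission are involved, but those patients matter most to 1E and 2E.

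The transfusion point holds in a limited form: on its plain reading, the 24-hour count gives a low value to a patient who bleeds to death early. The effect could be trivial or large, and the figures above only illustrate it. A count of all 24-hour deaths should not be set against the number of massive transfusions as if each were a missed event. Some of those patients die of brain injury, and some reach the threshold before dying.

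**What to change.** 1. Reconcile the synopsis, 7.2 and 7.3 so that eligibility for air-ambulance patients is fixed at enrolment by planned conveyance to a study site, as 7.2 already has it.
2. State in 9.7 that death before admission is an outcome and not a ground for retrospective exclusion. Report how many prehospital-sampled patients died before admission, so that the size of the issue becomes known.
3. Keep the 24-hour product count as stated. For the Aim 3 massive-transfusion analysis, add one supportive analysis in which death within 24 hours, before the threshold is reached, is a competing event or part of a composite, with the components reported separately.

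The cost is a wording change in four places and one added analysis. Keeping the existing outcome preserves continuity with a study active since 2008. One practical cost remains: 9.4.4 describes recording transfusion in the emergency department and theatre, so for patients who die before admission the products given would have to come from the prehospital record. If the composite is used, it mixes two kinds of event, which is why its components must be shown.
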